5. TREATMENT

5.1. Treatment Assignment

5.1.1. Subject Numbering and Treatment Assignment

Study sites will enter subject demographic and baseline data into the IWRS in order to receive a subject number and treatment allocation.

All subject numbers will be 6 digits; the first 3 digits will be the site number, and the last 3 digits will be the subject's number. This subject number will be maintained throughout the study and will not be reassigned. Subjects who withdraw consent or discontinue from the study after being assigned a subject number will retain their initial number.

Site staff will contact the IWRS to allocate the subject to treatment assignment and obtain the initial study treatment assignment. The investigator or designee will select the assigned bottles of study treatment from their stock that correspond to the number provided by the IWRS and dispense the study treatment to the subject. All subsequent dispensing of study treatment should follow this process. Refer to the IWRS Manual for detailed information.

If a subject is mistakenly given a bottle of study treatment that is not the bottle assigned by the IWRS, the IWRS help desk must be notified immediately. The reason for the misallocation of the study treatment must be documented by the study site and reported to the IRB/IEC.

For subjects who signed an ICF but are not allocated study treatment and for subjects who are allocated study treatment but were not treated, refer to the eCRF Completion Guidelines for instruction on which eCRFs to complete.

5.1.2. Randomization and Blinding

Not applicable.

5.2. INCB050465

5.2.1. Description and Administration

Details of INCB050465 are shown in [Table 2](#).

Table 2: Description and Administration of INCB050465

Compound Name	INCB050465
Dose strengths	1 mg, 2.5 mg, 5 mg, and 20 mg
Form	Tablet
Active compound	INCB050465
Route of administration	Oral
Dose and regimen for Treatment A	20 mg QD for 8 weeks followed by 20 mg once weekly
Dose and regimen for Treatment B	20 mg QD for 8 weeks followed by 2.5 mg QD
Instructions	INCB050465 will be taken orally with water without regard to food [REDACTED] INCB050465 should be taken at approximately the same time each day.

For QD administration, if a dose is missed by more than 12 hours, then the subject should skip the dose and take the next scheduled dose at the usual time. For once-weekly dosing, if the dose is missed by more than 2 days, then the subject should skip the dose and take the next scheduled dose.

5.2.2. Supply, Packaging, and Labeling

INCB050465 will be provided as 1 mg, 2.5 mg, 5 mg, and 20 mg tablets packaged in high-density polyethylene bottles. No preparation is required.

All Incyte investigational product labels will be in the local language and will comply with the legal requirements of each country.

Pneumocystis jirovecii pneumonia prophylaxis is required as coadministration with INCB050465. The prophylactic agents will be obtained from commercial supplies and will be reimbursed by Incyte. Investigators are responsible for ensuring that subjects receive commercially available supplies of the selected prophylactic agents as required per Protocol. The contents of the label will be in accordance with all applicable regulatory requirements. Further details are available in Section 5.6.1 and the Pharmacy Manual.

5.2.3. Storage

Bottles of INCB050465 should be stored at ambient conditions (15°C to 30°C or 59°F to 86°F).

5.2.4. Instruction to Subjects for Handling INCB050465

The subject must be instructed in the handling of INCB050465 as follows:

- To store study treatment at room temperature.
- To remove from the study treatment bottle only the number of tablets needed at the time of administration.
- Not to remove doses in advance of the next scheduled administration.

- To make every effort to take doses on schedule.
- To report any missed doses.
- To keep INCB050465 in a safe place and out of reach of children.
- To bring all used and unused study treatment kits to the site at each visit.

5.3. Treatment Compliance

Compliance with all study-related treatments should be emphasized to the subject by the site personnel, and appropriate steps should be taken to optimize compliance during the study. Compliance with study treatment will be calculated by the sponsor based on the drug accountability documented by the site staff and monitored by the sponsor/designee (tablet counts). Subjects will be instructed to bring all study treatments with them to the study visits in order for site personnel to conduct tablet counts to assess study treatment accountability. The drug accountability documentation will be used by the sponsor to calculate treatment compliance.

5.4. Treatment Interruptions and Adjustments

5.4.1. Criteria and Procedures for Dose Interruptions and Reductions of INCB050465

Treatment with INCB050465 may be interrupted for up to 14 days to allow for resolution of toxicity. Subjects may resume treatment if no medical condition or other circumstance exists that, in the opinion of the investigator, would make the subject unsuitable for further participation in the study. The treating investigator should contact the sponsor to discuss the case of any subject whose treatment has been interrupted for more than 14 days before restarting treatment with INCB050465.

5.4.1.1. Dose Modifications

Dose modification guidance for AEs that have been previously observed in subjects receiving INCB050465 or are potential class-effect AEs are provided (see [Table 3](#) and [Table 5](#)). The starting dose and dose reduction levels of INCB050465 are provided (see [Table 4](#)). Individual decisions regarding dose interruption and reduction should be made using clinical judgment and in consultation with the sponsor's medical monitor, taking into account relatedness of the AE to the study treatment and the subject's underlying condition. Adverse events that have a clear alternative explanation or transient (≤ 72 hours) abnormal laboratory values without associated clinically significant signs or symptoms may be exempt from dose reduction guidelines.

Table 3: Guidelines for Interruption and Restarting INCB050465

ADVERSE EVENT	ACTION TAKEN
Chemistry	

 Grade 3 AST and/or ALT ($> 5.0 \times \text{ULN}$). 
Note: In subjects with liver metastasis-related elevations at baseline, contact sponsor to discuss clinical management and possible dose reductions.
	
Step 1: Interrupt INCB050465 and monitor weekly until the toxicity has resolved to \leq Grade 1.
 
Step 2: Restart INCB050465 at next lower dose with medical monitor approval. Monitor as clinically indicated.

Hematology	

 Grade 3 ANC ($< 1.0 \times 10^9/\text{L}$). Grade 2 platelet count (50 to $< 75 \times 10^9/\text{L}$) for subjects who enrolled with platelets $> 100 \times 10^9/\text{L}$. Grade 3 platelet count ($< 50 \times 10^9/\text{L}$) for subjects who enrolled with platelets $\leq 100 \times 10^9/\text{L}$. 	
Step 1: Interrupt INCB050465 up to 14 days until the toxicity has resolved to \leq Grade 1 or pretherapy baseline. For Grade 3 ANC, monitor at least weekly.
 
Step 2: Restart INCB050465 at same dose; monitor as clinically indicated.

 Grade 4 ANC ($< 0.5 \times 10^9/\text{L}$). Grade 3 or Grade 4 febrile neutropenia. Platelet count is Grade 4 ($< 25 \times 10^9/\text{L}$). 	
Step 1: Interrupt INCB050465 up to 14 days until the toxicity has resolved \leq Grade 2. (Monitor at least weekly.)
 
Step 2: Restart INCB050465 at same dose. Monitor as clinically indicated. If reoccurs, restart at next lower dose.

Other toxicities	

 Diarrhea/colitis. 	See Table 5 .

 Pneumonitis (Grade 1). 	
Step 1: Interrupt INCB050465 until the toxicity has resolved.
 
Step 2: Restart INCB050465 at next lower dose. Monitor as clinically indicated.

 Pneumonitis (Grade ≥ 2). 	Permanently discontinue INCB050465.

 Skin toxicity (eg, rash, pruritus, unless otherwise specified; Grade 2 and 3). 	
Step 1: Interrupt INCB050465 until the toxicity has resolved to \leq Grade 1.
 
Step 2: Restart INCB050465 at same dose. If assessed as related to INCB050465, restart at next lower dose.

 Exfoliative dermatitis (Grade 1). 	
Step 1: Interrupt INCB050465 until the toxicity has resolved.
 
Step 2: Restart INCB050465 at next lower dose. Monitor as clinically indicated.

 Exfoliative dermatitis (\geq Grade 2). 	Permanently discontinue INCB050465.

 Intestinal perforation (any grade). 	Permanently discontinue INCB050465.

 PJP infection. 	Interrupt INCB050465. Permanently discontinue INCB050465 if PJP infection is confirmed.

 CMV infection. 	Subjects with CMV viremia without associated clinical signs of CMV infection should be carefully monitored. Consider interrupting INCB050465 for subjects with CMV viremia and clinical signs of infection until the infection has resolved. Restart INCB050465 reduced by 1 dose level if approved by the medical monitor.

Table 3: Guidelines for Interruption and Restarting INCB050465 (Continued)

ADVERSE EVENT	ACTION TAKEN
• Varicella zoster infection.	Interrupt INCB050465. Restart INCB050465 only by approval of the medical monitor.
• Any Grade 1 or Grade 2 toxicity unless otherwise specified.	Continue INCB050465 and treat the toxicity; monitor as clinically indicated.
• Any Grade 3 toxicity, if clinically significant and not manageable by supportive care unless otherwise specified.	Step 1: Interrupt INCB050465 up to 14 days until the toxicity has resolved to \leq Grade 1. Step 2: Restart INCB050465 at same dose. If assessed as related to INCB050465, restart at next lower dose. If interrupted for > 14 days, contact the medical monitor for approval to restart INCB050465. Monitor as clinically indicated.
• Any recurrent Grade 3 toxicity after 2 dose reductions.	Discontinue INCB050465 administration and follow-up per Protocol. Exceptions require approval of sponsor.
• Any other Grade 4 toxicity.	Discontinue INCB050465 administration and follow-up per Protocol. Exceptions require approval of sponsor.

ALT = alanine aminotransferase; AST = aspartate aminotransferase; CMV = cytomegalovirus; IV = intravenous; ULN = upper limit of normal.

Table 4: Dose Levels and Reductions for INCB050465

Timepoint	Treatment A	Treatment B
Starting dose	20 mg QD for 8 weeks (Day 1 through Day 56)	20 mg QD for 8 weeks (Day 1 through Day 56)
First dose reduction	10 mg QD	10 mg QD
Second dose reduction	5 mg QD	5 mg QD
Week 9 (Day 57) onward	20 mg once weekly ^a	2.5 mg QD ^b
First dose reduction	10 mg once weekly	1 mg QD ^c
Second dose reduction	5 mg once weekly	NA

^a All subjects will receive 20 mg once weekly at Week 9 (Day 57) regardless of prior dose level, unless a dose modification of a switch to a QW schedule before Week 9 is required for diarrhea/colitis management (see Table 5).

^b All subjects will receive 2.5 mg QD at Week 9 (Day 57) regardless of prior dose level, unless a dose modification of a switch to a QW schedule is required for diarrhea/colitis management (see Table 5).

^c Further dose modification due to diarrhea or colitis for subjects on 1 mg QD is permitted (see Table 5).

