INCB050465 is being evaluated as a monotherapy in a Phase 1/2, dose-escalation and expansion study (INCB 50465-101, NCT02018861; Phillips et al 2016). As of 18 AUG 2017, data were available for 72 subjects who received INCB050465 administered orally at QD doses of 5 mg (n = 1), 10 mg (n = 3), 15 mg (n = 3), 20 mg (n = 34), 30 mg (n = 27), and 45 mg (n = 4). The median duration of treatment was 122.5 days (range: 7-690). Adverse events observed in \geq 20% of subjects were nausea (36%), diarrhea (35%), fatigue and rash (each 31%), and cough and vomiting (each 24%). New or worsening \geq Grade 3 anemia, thrombocytopenia, and neutropenia occurred in 7%, 10%, and 20% of subjects, respectively. No \geq Grade 3 nonhematological treatment-related AEs were reported in \geq 10% of subjects. Serious AEs that occurred in \geq 2 subjects included diarrhea (n = 5); pyrexia (n = 4); colitis, sepsis, and hypotension (n = 3 each); and ventricular tachycardia, pneumonia, exfoliative dermatitis, respiratory failure, syncope, urinary tract infection, bronchitis, and bacteremia (n = 2 each). Fourteen (19%) of the 72 subjects discontinued study treatment due to the following 10 AEs: diarrhea (n = 3); exfoliative dermatitis and colitis (n = 2 each); and pneumonitis, rash, psoriasis, neutropenia, pleural effusion, cytomegalovirus colitis, and hypercalcemia (n = 1 each). No liver function test abnormalities > Grade 1 were reported while subjects were receiving study treatment. No dose-limiting toxicities were identified, and the maximum tolerated dose was not reached.

Pharmacokinetics analysis showed the t_{max} is 0.5 to 1 hour, the terminal half-life is approximately 8 to 12 hours, and exposure appeared to be dose-proportional between 5 mg QD and 45 mg QD at steady state. The pharmacodynamic analyses demonstrated robust and sustained pathway inhibition at all dose levels tested (Phillips et al 2016). Refer to the IB for further details (IB).

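### Table 3 gives participants enrolled with platelets above 100 × 10⁹/L no haematology-row hold at 25 to <50, so the written prompt to interrupt is weaker at a count of 40 than at 60.

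*Protocol*

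**What the plan says.** Protocol Section 5.4.1.1, Table 3, has three platelet entries under Hematology. Two share the first row with an ANC trigger:

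- Enrolled above 100 × 10⁹/L: "Grade 2 platelet count (50 to $< 75 \times 10^9/\text{L}$) for subjects who enrolled with platelets $> 100 \times 10^9/\text{L".
- Enrolled at 100 × 10⁹/L or below: "Grade 3 platelet count ($< 50 \times 10^9/\text{L}$) for subjects who enrolled with platelets $\leq 100 \times 10^9/\text{L".

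The action for that row carries no clinical condition: "Interrupt INCB050465 up to 14 days until the toxicity has resolved to \leq Grade 1 or pretherapy baseline", followed by restart at the same dose. The third entry, in the next row, is a Grade 4 count below 25 at any enrolment level, also with interruption: "Interrupt INCB050465 up to 14 days until the toxicity has resolved \leq Grade 2. (Monitor at least weekly".

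The continuation of Table 3 has a general row for "Any Grade 3 toxicity, if clinically significant and not manageable by supportive care unless otherwise specified". It allows a hold of up to 14 days until Grade 1 or better and restart at the same dose, with this qualification: "If assessed as related to INCB050465, restart at next lower dose. If interrupted for > 14 days, contact the medical monitor for approval".

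The lead-in covers the whole table: "Individual decisions regarding dose interruption and reduction should be made using clinical judgment and in consultation with the sponsor's medical monitor". Section 5.4.1 separately permits an interruption of up to 14 days for toxicity. Section 5.4.3 tells investigators what to advise participants about cytopenias and gives no dosing rule.

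**The concern.** A dose-hold rule should not weaken as the laboratory value worsens. Here, within the group enrolled above 100, it does so between 50 and 25 and then strengthens again below 25. At the same count of 40, the participant who has fallen further from the enrolment value gets the weaker prompt.

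No rationale for this appears in the documents, and the layout suggests a drafting slip. Of the three triggers in the first haematology row, ANC below 1.0 and platelets below 50 have no lower limit; only the one for enrolment above 100 stops, at 50.

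What is at stake is the consistency of a safety rule across approximately 100 sites (Section 4.3.1), for a toxicity that Section 5.4.3 describes as an apparent class effect. An investigator who kept dosing at 40 in a participant without bleeding would be following the table as printed.

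**Working it through.** The plan states no figure to reproduce. The check is to trace platelet counts through Table 3 by enrolment group.

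**Inputs (all × 10⁹/L).** Enrolment floor: 50 (Section 3.1, criterion 8c), so both groups can enrol. Triggers: 50 to <75 if enrolled >100; <50 if enrolled ≤100; <25 for all. Where no haematology entry matches, the general Grade 3 row or the general Grade 1/2 row (continue and treat) applies.

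**Trace, taking each count as the first abnormal one seen.**

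| Count | Enrolled >100 | Enrolled at 90 |
|---|---|---|
| 60 | First haematology row: interrupt; restart at same dose | No platelet trigger: continue |
| 40 | No haematology row. General Grade 3 row: interrupt only if clinically significant and not manageable with supportive care; next lower dose if related | First haematology row: interrupt; restart at same dose |
| 20 | Grade 4 row: interrupt; restart at same dose, lower if it recurs | Interrupt (both haematology rows match) |

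Stepping through whole-number counts from 0 to 74 at an enrolment count of 150 leaves 25 to 49 as the only values without a haematology row. The uncovered band is 25 to <50, a width of 50 − 25 = 25.

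**Could Grade 2 be read as Grade 2 or worse?** The bullet prints a closed range. Elsewhere Table 3 marks an open-ended grade explicitly, as for pneumonitis and exfoliative dermatitis at Grade 2 or above.

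**Can a count first be seen below 50?** Yes. Scheduled haematology is every 2 weeks for the first 8 weeks, every 4 weeks through Week 48 and every 12 weeks after that (Synopsis; Table 7). A count can pass through 50 to <75 between draws. Unscheduled tests are allowed (Section 6.6), but they do not change which row applies once the count is known.

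**Who is not affected?** A participant held at 60 who then falls to 40 remains held, because the first-row exit is Grade 1 or better (75 or above) or pretherapy baseline. With enrolment above 100, a count of 40 meets neither.

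**After the proposed change.** With the bullet at 25 to <75, every count below 75 in the group enrolled above 100 has a haematology row, and 40 gets the same hold as 60.

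**The case against.** The strongest reply is that Table 3 is guidance under clinical judgment with medical-monitor consultation, that Section 5.4.1 permits a hold with no grade condition, and that most investigators would probably hold at 40. This stands, and it limits the weight of the point. It also means the contrast should not be read as automatic at 60 against optional at 40: the same discretion covers every row. But these provisions only permit a hold. They do not prompt one, and prompting is the purpose of the table.

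A second reply is that a default exists, namely the general Grade 3 row, and that it is stricter in one respect: a related event restarts at the next lower dose, and a hold beyond 14 days needs medical-monitor approval to restart. Both statements are correct. A reader might infer that the whole pathway is more lenient at 40; it is not. Only the condition for starting the hold is weaker, and the restart terms matter only once a hold has begun.

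A reader might also see an error in the Grade 4 row, since restart at Grade 2 or better (from 50) overlaps the 50 to <75 trigger. The documents do not support that. Each row can carry its own exit, Grade 4 ANC has the same looser exit, and Appendix E (Amendment 2, item 3) shows that the level was chosen deliberately to match eligibility.

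**Conclusion.** The gap is real but minor. For participants enrolled above 100 × 10⁹/L whose first observed abnormal count is 25 to <50, the table's prompt to interrupt is conditional, although it is unconditional at 50 to <75, below 25, and at 25 to <50 in those enrolled at 100 or less. This rests on reading the bullets as printed; they are legible and show no sign of redaction.

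The number affected cannot be derived. Section 1.3 reports that in the Phase 1/2 study new or worsening Grade 3 or higher anaemia, "thrombocytopenia, and neutropenia occurred in 7%, 10%, and 20% of subjects, respectively". The 10% for thrombocytopenia is context only. A reader might convert it to 7 of 72 and scale it to 90 participants as an upper limit, but two things prevent this. The 20% for neutropenia in the same sentence matches no count out of 72 (14/72 = 19.4%, 15/72 = 20.8%), so the denominator is uncertain. And a rate from a study with other doses and several lymphoma types does not bound the rate here. It also mixes in Grade 4 events and participants enrolled at 100 or less.

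Nothing here affects the ORR analysis, the sample size or the futility rule.

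**What to change.** In the first haematology row of Table 3, change the bullet for enrolment above 100 × 10⁹/L so that it covers Grade 2 or Grade 3 counts, with the range 25 to <75 × 10⁹/L.

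In the action cell, state whether a related Grade 3 count in this group restarts at the next lower dose, as it now would under the general Grade 3 row, or at the same dose, as for those enrolled at 100 or less. Without that statement the change would silently remove the existing dose reduction for related Grade 3 events. Either choice is the sponsor's to make.

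The Grade 4 row needs no change. The cost is one bullet and one sentence in an amendment or clarification letter, and a few more holds.

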5.4.2. Supportive Care Guidelines for Diarrhea/Colitis

Subjects should be informed to immediately report to the investigator any event of diarrhea. Treatment with INCB050465 may be interrupted or modified according to the guidelines in Table 5 to allow for resolution of diarrhea/colitis.

Subjects should receive appropriate supportive care measures as deemed necessary by the investigator. For any \geq Grade 1 diarrhea, subjects should be advised to drink liberal quantities of clear fluids. If sufficient oral fluid intake is not feasible, fluid and electrolytes should be substituted via IV infusion. Subjects should try to eat 5 to 6 small meals per day; low-fat,

high-protein foods; and cooked instead of raw vegetables. Subjects may supplement their diet with bananas, rice, applesauce, and toast to reduce the number of bowel movements and may also try crackers, gelatin, noodles, or oatmeal. Subjects should avoid fried, fatty, greasy, or spicy foods; milk, milk products, and acidic drinks; high-fiber foods and foods that cause gas; and alcohol, caffeine, and herbal supplements (Coutré et al 2015).

For each occurrence, attempts should be made to rule out other causes, such as metastatic disease or bacterial or viral infection (including CMV), which might require additional supportive care.

It may be necessary to perform conditional procedures such as colonoscopy with biopsy as part of evaluation of the event. Note that several courses of steroid tapering may be necessary as symptoms may worsen when the steroid dose is decreased.

Subjects should be carefully monitored for signs and symptoms of enterocolitis (such as diarrhea, abdominal pain or cramping, blood or mucus in stool, with or without fever) and of bowel perforation (such as peritoneal signs and ileus).

Table 5: Guidelines for Dose Modification of INCB050465 for Diarrhea/Colitis

ADVERSE EVENT	ACTION TAKEN

 • Diarrhea (Grade 1). 	
Step 1: Treat with antimotility agents (eg, 4 mg loperamide followed by 2 mg every 4 hours or after every unformed stool) and initiate supportive care (see Section 5.4.2). Monitor approximately every 48 hours until resolved. If not improved after 48 hours, treat per guidance for Grade 2.


 • Diarrhea (Grade 2). 	
Step 1: Interrupt INCB050465. Perform work-up for infection (including CMV, C. difficile, etc) immediately. Initiate or continue supportive care (see Section 5.4.2). Monitor approximately every 48 hours until resolution.
 
Step 2: If improved within 48 hours and/or infection* is confirmed, restart INCB050465 at the same schedule and dose after resolved to \leq Grade 1 and continue to monitor.
 
*For infectious diarrhea/colitis, follow institutional standard-of-care guidelines and restart INCB050465 according to clinical judgement after resolved to \leq Grade 1. Consult with medical monitor if needed.
 
Step 3: If not improved within 48 hours and infection is ruled out, start oral steroids, or consider IV steroids if participant is being given IV fluids. If no improvement with oral steroids, switch to IV steroids.
 
Step 4: When diarrhea resolves to \leq Grade 1, continue supportive care and taper steroids according to institutional standard of care. When taper is complete (eg, no steroid or \leq 10 mg/day prednisone or equivalent) and diarrhea is \leq Grade 1, restart INCB050465 at the next lower dose with approval of the medical monitor (see Table 4 for dose levels).
 
Step 5: If Grade 2 diarrhea reoccurs, treat per guidance for diarrhea (\geq Grade 3)/noninfectious colitis.
 
Step 6: If \geq Grade 2 diarrhea reoccurs a third time, permanently discontinue INCB050465.

Table 5: Guidelines for Dose Modification of INCB050465 for Diarrhea/Colitis (Continued)

ADVERSE EVENT	ACTION TAKEN								

 • Diarrhea (≥ Grade 3). • Noninfectious colitis (any grade; confirmed or suspected). 	
Step 1: Interrupt INCB050465. Perform work-up for infection (including CMV, C. difficile, etc) immediately. Initiate or continue supportive care (see Section 5.4.2). Consider colonoscopy with biopsy for diarrhea ≥ Grade 3 and/or if symptoms^a suggestive of colitis. Monitor every 48 hours until resolution.
 
Step 2: If infection* is ruled out, start oral steroids, or consider IV steroids if participant is being given IV fluids. If no improvement with oral steroids within 48 hours, switch to IV steroids.
 
*For infectious diarrhea/colitis, follow institutional standard of care guidelines and restart parasclisib according to clinical judgement after resolved to ≤ Grade 1. Consult with medical monitor if needed.
 
Step 3: When diarrhea/colitis resolves to ≤ Grade 1, continue supportive care and taper steroids according to institutional standard of care. When taper is complete (eg, no steroid or ≤ 10 mg/day prednisone or equivalent) and diarrhea/colitis is ≤ Grade 1, restart INCB050465 as described herein and with approval of the medical monitor. Continue to monitor.
 
  
 INCB050465 Current Dose	Dose Modification	
   
 Any dose with QD dosing	20 mg QW regardless of Treatment A or B assignment	
 
 20 or 10 mg QW	Restart next lower dose	
 
 5 mg QW	Permanently discontinue	
  
 
Step 4: If ≥ Grade 3 diarrhea/colitis (any grade) reoccurs, permanently discontinue INCB050465.
	INCB050465 Current Dose	Dose Modification	Any dose with QD dosing	20 mg QW regardless of Treatment A or B assignment	20 or 10 mg QW	Restart next lower dose	5 mg QW	Permanently discontinue
INCB050465 Current Dose	Dose Modification								
Any dose with QD dosing	20 mg QW regardless of Treatment A or B assignment								
20 or 10 mg QW	Restart next lower dose								
5 mg QW	Permanently discontinue								

^a Diarrhea accompanied by abdominal pain and/or mucus or blood in stool.

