1.5. Potential Risks and Benefits of the Treatment Regimen

INCB050465 has effects on the immune system. Therefore, subjects in this study will be monitored closely for evidence of infections or new cancers, and study treatment administration will be discontinued if there is evidence of clinically significant infection or new cancer.

While PJP has not been reported with the use of INCB050465 either as monotherapy or in combination therapy, subjects who receive INCB050465 in this study will receive PJP prophylaxis. Subjects will be asked to report all sulfa drug allergies and those allergic to standard PJP prophylaxis with sulfonamide antibiotics will receive either inhaled pentamidine or atovaquone for PJP prophylaxis; these subjects will not be given dapsone.

As presented in Section 1.3, the most common AEs ($\geq 20\%$) observed with INCB050465 monotherapy have been nausea, diarrhea, fatigue, cough, rash, and vomiting. Serious AEs (≥ 2 subjects) have included colitis, diarrhea, sepsis, hypotension, ventricular tachycardia, pyrexia, respiratory failure, pneumonia, bronchitis, exfoliative dermatitis, syncope, urinary tract infection, and bacteremia. Dose modification guidance and supportive care guidelines for diarrhea/colitis are implemented in this study.

Based on efficacy and safety data from the ongoing Study INCB 50465-101, which evaluated a continuous 20 mg QD dose regimen, the treatment regimen for Study INCB 50465-204 will be 20 mg QD for 8 weeks, followed by either 20 mg once weekly or 2.5 mg QD of INCB050465. As detailed in Section 1.3, these regimens are proposed to assess whether the frequency of AEs leading to treatment withdrawal will be reduced while maintaining PI3K pathway inhibition and maintenance of response.

INCB050465 is metabolized primarily by CYP3A4; therefore, use of any potent CYP3A4 inhibitors or inducers within 14 days or 5 half-lives (whichever is longer) before the first dose of INCB050465 will be prohibited.

The effects of INCB050465 on fetal development has not been evaluated nor is it known whether INCB050465 passes into human breast milk; therefore, subjects who are pregnant or breastfeeding are excluded from participation in this study.

There are no preclinical data available to date on the potential phototoxicity of INCB050465. Therefore, subjects enrolled in this study taking INCB050465 will be instructed by the site staff

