5.6.2. Restricted Medications

- Use of systemic corticosteroid doses ≤ 10 mg/day prednisone (or equivalent) is permitted but discouraged from the screening visit through EOT.
- Short courses of systemic corticosteroid doses > 10 mg/day prednisolone or equivalent are permitted only in the case of severe or life-threatening complications, which cannot be controlled with other drugs, but are otherwise discouraged from the screening visit through EOT.
- Use of weak or moderate inducers or inhibitors of CYP3A4 (see Appendix D) is discouraged, and investigators should seek other options where possible.

- Use of P-glycoprotein substrates of clinical relevance should be used with caution (ie, aliskiren, ambrisentan, colchicine, dabigatran etexilate, digoxin, everolimus, fexofenadine, imatinib, lapatinib, maraviroc, nilotinib, posaconazole, ranolazine, saxagliptin, sirolimus, sitagliptin, talinolol, tolvaptan, topotecan) from the screening visit through the EOT visit.
- Localized radiotherapy will be permitted if administered as treatment for pain or impending compression fractures and with prior approval of the medical monitor.

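### Confirmed CMV diarrhea meets protocol instructions that disagree on interruption, restart dose and approval, with no statement of which governs

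*Protocol*

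**What the plan says.** Four places in the protocol bear on a subject with confirmed CMV diarrhea or colitis.

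- **Table 5 (Section 5.4.2), Grade 2 diarrhea.** Step 1 interrupts treatment and orders an infection work-up: "Perform work-up for infection (including CMV" and other pathogens. Step 2 reads "If improved within 48 hours and/or infection* is confirmed, restart INCB050465 at the same schedule and dose", conditional on improvement to Grade 1 or better. The asterisk note in that cell tells the site, for infectious cases, to "follow institutional standard-of-care guidelines and restart INCB050465 according to clinical judgement after resolved to" Grade 1 or better, and to consult the medical monitor if needed.
- **Table 5, Grade 3 or higher diarrhea and noninfectious colitis.** Step 1 again interrupts. Infectious cases get the same clinical-judgement note. There is no same-dose instruction.
- **Table 3 (Section 5.4.1.1), CMV row.** For viremia with clinical signs: "Consider interrupting INCB050465 for subjects with CMV viremia and clinical signs of infection until the infection has resolved". Then: "Restart INCB050465 reduced by 1 dose level if approved by the medical monitor".
- **Section 1.5.** The risk text states that "study treatment administration will be discontinued if there is evidence of clinically significant infection or new cancer".

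Table 3 sends diarrhea/colitis to Table 5 but keeps its separate CMV row. The mandatory discontinuation list in Section 5.5.1 does not name infection.

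On steroids, Table 5 starts them for Grade 2 diarrhea that has not improved within 48 hours once infection is ruled out. Section 5.6.2 says: "Short courses of systemic corticosteroid doses > 10 mg/day prednisolone or equivalent are permitted only in the case of severe or life-threatening complications".

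**The concern.** A subject with confirmed CMV diarrhea meets both the CMV row of Table 3 and a diarrhea row of Table 5, and the two do not give the same answer. Two sites could treat the same event differently, and both could be following the protocol.

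Two things are at stake. The first is consistent handling of a serious infection already seen with this drug: CMV colitis is among the events that led to discontinuation in study 101 (Section 1.3). The second is the meaning of the safety tables. Colitis, diarrhea and CMV infection are events of special interest (Protocol Section 8.5, SAP Section 9.2.2). Dose reductions, interruptions and discontinuations because of adverse events are tabulated (Protocol Section 9.4.2.1, SAP Section 9.2.3). Fewer withdrawals for adverse events is the stated reason for both maintenance regimens (Sections 1.4 and 1.5), although it is not the primary objective, which is ORR. If the dose action depends on which passage was applied, part of those rates reflects the wording and not the drug.

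**Working it through.** This is a check of text against text. The plan gives no figure to reproduce.

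**Step 1. Does confirmed CMV fall under Table 5?** Yes. The work-up names CMV, so a positive result meets the condition that infection is confirmed.

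**Step 2. Confirmed Grade 2 CMV diarrhea, side by side.**

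| Question | Table 5, Steps 1-2 | Table 5, asterisk note | Table 3, CMV row |
|---|---|---|---|
| Interrupt? | Required | Not restated | To be considered |
| Restart when? | Diarrhea Grade 1 or better | Grade 1 or better | Infection resolved |
| Restart dose | Same dose and schedule | Clinical judgement | One level lower |
| Medical monitor | Not mentioned | Consult if needed | Approval required |

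Tables 3 and 5 differ on all four rows. Table 5 also differs from its own note on the restart dose.

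**Step 3. Grade 3 or higher CMV diarrhea, and CMV colitis.** The same-dose instruction is absent. What remains is Table 3 (one level lower, approval required) against the Table 5 note (clinical judgement, consult if needed).

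**Step 4. Does any text set an order of precedence?** No. Table 3 refers diarrhea/colitis to Table 5, but the CMV row carries no cross-reference. Section 5.4.1.1 asks for clinical judgment in consultation with the medical monitor when doses are interrupted or reduced. It covers both tables without ranking them, and it treats consultation as part of the decision where the Table 5 note makes it optional.

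**Step 5. Section 1.5.** Discontinuation for clinically significant infection does not match the restart that Table 3 allows after CMV infection, or after varicella zoster with medical monitor approval. Section 5.5.1 does not carry it as a named criterion.

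**Step 6. Steroids.** Table 5, Grade 2, Step 4 treats a taper as complete at no steroid or at 10 mg/day or less of prednisone or equivalent. That endpoint implies that higher doses are used for Grade 2 diarrhea. Section 5.6.2 reserves doses above 10 mg/day for severe or life-threatening complications. This conflict concerns noninfectious cases and is separate from CMV.

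**Step 7. Size.** Input: 1 of 72 subjects in study 101 discontinued for CMV colitis (Section 1.3).

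- Rate: 1/72 = 1.4%; exact 95% CI 0.04% to 7.5%.
- Carried over to 90 subjects: 90 × 1/72 = 1.25; with the interval limits, 90 × 0.0004 ≈ 0 to 90 × 0.075 ≈ 7.

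This counts only CMV colitis leading to discontinuation, so it leaves out CMV events managed by interruption or reduction. It also assumes that a rate from continuous daily dosing applies here. In study 101, 27 + 4 = 31 of 72 subjects received 30 or 45 mg QD, above the 20 mg used in this trial.

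**The case against.** The strongest reply is that the protocol leaves these decisions to clinical judgment with the medical monitor. Restart by clinical judgement does not exclude a one-level reduction, so the Table 5 note and the Table 3 row can be read together on dose. That is fair for Grade 3 or higher diarrhea and for CMV colitis, where the remaining difference is mainly whether the reduction and the approval are required. It does not remove the literal same-dose wording in the Grade 2 row, or the difference between approval and consultation if needed.

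On Section 1.5, it is fair to say that this is introductory risk text, that it depends on the infection being clinically significant, and that it does not say permanently, a word Tables 3 and 5 use when they mean it. The general criteria in Section 5.5.1 could also cover a serious infection. The mismatch is therefore secondary, but it still needs aligning.

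On steroids, an event-specific table can be read as overriding a general restriction. Nothing in the text says so, and a cross-reference would settle it.

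Three stronger readings are tempting and are not supported:

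- A reader might infer that every CMV diarrhea or colitis case faces a same-dose rule. That wording is only in the Grade 2 diarrhea row.
- A reader might take "If not improved after 48 hours, treat per guidance for Grade 2" in the Grade 1 row to mean that restarting at Grade 1 itself triggers a new interruption. A subject restarted after Grade 2 has already improved and stays under the Grade 2 row, which gives its own next steps for monitoring and recurrence. Nothing sends that subject back to the Grade 1 row.
- A reader might size the problem from the 35% diarrhea rate in study 101 (0.35 × 90 = 31.5 subjects). That is any-cause, any-grade diarrhea and says nothing about CMV. Scheduled CMV DNA testing does not make the conflict certain either, because Table 3 only monitors viremia without clinical signs.

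**Conclusion.** The inconsistency is real and is clearest for confirmed Grade 2 CMV diarrhea, where Table 5, its own note and the Table 3 CMV row cannot all be followed. For Grade 3 or higher CMV diarrhea and for CMV colitis it is narrower: a required one-level reduction with approval against restart by judgement. The Section 1.5 statement and the steroid wording are lesser, separate mismatches.

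Few subjects are likely to be affected, about 1 per 90 with a range of roughly 0 to 7, on the assumption that the study 101 rate carries over. The effect on the tabulated dose-action rates would therefore be small. No regimen comparison is planned (SAP Section 3.2) and the primary endpoint is ORR, so this does not threaten the main efficacy conclusion. The case for correcting it rests on consistent handling of a serious event and on the low cost of doing so. The documents do not show which instruction is intended, and this review takes no view on that.

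**What to change.** Amend the protocol so that these passages agree:

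1. State in Tables 3 and 5 which table governs when the confirmed infection is CMV.
2. Give one answer on interruption, restart threshold, restart dose and medical monitor approval wherever CMV diarrhea or colitis is covered, including Table 5 Step 2 and its asterisk notes.
3. Align the Section 1.5 statement on clinically significant infection with Section 5.5.1 and Table 3.
4. Reconcile Section 5.6.2 with the Table 5 steroid steps.

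The sponsor's medical team decides which rule stands in each case. The cost is cross-references and wording in an amendment, plus notice to sites. It adds no visits, tests or analyses.
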